5.1.1.1 Collection of VOC

A VOC occurring during the study should be recorded by the Investigator both as a primary endpoint event, and also as an AE. A potential VOC judged by the Investigator not to fulfil the definition of the primary endpoint should be also recorded as an AE according to standard AE reporting procedures (see Section 6).

Collection of some information related to the potential VOC should be done by the patient/caregiver in real-time in the eDevice, and not based on recollection at the next planned visit. When information related to a potential VOC is entered in the eDevice, the Investigator will be alerted and should, unless a contact already occurred, call the caregiver within 72 hours from the onset of the potential event to enable a medical consultation and event data collection (see [Appendix D](#), Interview Guide for VOC-triggered Telephone Calls). Families

will be instructed to call the site in case of a VOC, unless already contacted by the site within 72 hours.

Regardless of primary setting of treatment (eg, in-patient hospitalisation, short-stay outpatient unit, emergency department or self-treated), some VOC-related information outlined below must be documented by the caregiver in the patient's eDevice. The Investigator only, will judge if the potential VOC fulfil the definition of VOC (see Section 5.1.1 for definition). If needed, the Investigator should request medical records and/or other documents from other medical facility than the study site. It will be the Investigators' responsibility to document the VOC in medical records and ensure that the VOC data in the eCRF is correct.

Following information will be captured in the eDevice to be reviewed by the Investigator:

- Start and stop date/time of the VOC event
- Assessment of worst pain intensity will be done once daily throughout the duration the VOC event (Patient/Observer Reported), see Section 5.1.2.
- Report of anatomical location(s) of pain will be done once daily throughout the duration of the VOC event (Patient/Observer Reported).
- If analgesics are taken during the VOC (Yes/No) and the Investigator will enter details of the analgesics (ie, name, type, dose, routes of administration, frequency) into the eCRF.

The following data should be collected in the eCRF, based on review of eDevice entries, information from the medical consultation and copies from other medical facilities:

- Confirmation if the event fulfils the VOC definition

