6.3.9 Vaso-occlusive crisis (VOCs) and acute SCD complications

A VOC and acute SCD complications (TIA/ischaemic stroke, hepatic sequestration and splenic sequestration, priapism and dactylitis) occurring during the study should be recorded by the Investigator as AEs. For a definition and collection of VOCs, see Section [5.1.1](#) and for acute SCD complication, see Section [5.1.5](#).

- A VOC fulfilling the criteria should also be recorded as an adverse event with the diagnosis Sickle cell anaemia with crisis.
- If the VOC event includes symptoms of other acute SCD complications, these should also be recorded, but separately from the VOC event in the eCRF.

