3.2 Primary Efficacy Variable

3.2.1 Vaso-occlusive Crises (VOCs)

A VOC event occurring during the study (following randomisation at Visit 2) and, as judged by the investigator to fulfil the definition of the primary endpoint event, should be recorded by the investigator both as a primary endpoint event on the VOC1 eCRF and as an adverse event (AE) on the AE eCRF.

The primary efficacy variable is the number of VOC events during the treatment period. The number of VOC events is defined as the count of VOC events experienced by a patient over the defined treatment period (refer to Section 3.1.4), as assessed by the investigator and collected on the VOC1 eCRF. Any VOC event identified outside the defined treatment period will not be included in the primary analysis.

A VOC is the composite of a painful crisis and/or an acute chest syndrome (ACS) event.

Each component is defined as:

- A painful crisis is an onset or worsening of pain that lasts at least 2 hours, for which there is no explanation other than vaso-occlusion and which requires therapy with oral or parenteral opioids, parenteral non-steroidal anti-inflammatory drugs (NSAIDs), or other analgesics prescribed by a healthcare provider in a medical setting (such as a hospital, clinic or emergency room visit) or at home.

- ACS is an acute illness characterised by fever and/or respiratory symptoms, accompanied by a new pulmonary infiltrate on a chest X-ray.

A VOC event is identified as follows:

- Within each of the two separate components: Event with an onset date ≤ 7 days of the previous event onset date will not be counted as a new event. It will be composed of the start date of the first occurrence of the component in the event to the stop date of the last occurrence of the component in the event.

For example: Patient 1: *Counted as 2 events not 3 individual events*

PAINFUL CRISIS	2019-07-24	2019-07-28
PAINFUL CRISIS	2019-10-22	2019-10-23
PAINFUL CRISIS	2019-10-28	2019-10-30

- Across the two separate components: Event with an onset date ≤ 7 days of the previous event onset date will not be counted as a new event. It will be composed of the start date of the first component in the event to the stop date of the last component in the event.

For example: Patient 2: *Counted as 4 events not 5 individual events*

ACUTE CHEST SYNDROME	2019-07-17	2019-07-23
PAINFUL CRISIS	2019-07-17	2019-07-23
PAINFUL CRISIS	2019-10-04	2019-10-04
PAINFUL CRISIS	2019-10-21	2019-11-05

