4.2.9.1 Adverse Events

Summary tables will include on-treatment/off-treatment AEs (refer to Section [3.4.1](#)) only, unless otherwise specified. That is, pre-treatment AEs will be included in the patient data listings only.

Separate overall summary tables will be produced for AEs on-treatment and off-treatment showing the number (n) and percentage (%) of patients with at least one AE in each of the following AE categories: Any AE, any AE causally related to study treatment, maximum AE intensity, any AE with an outcome of death, any SAE and discontinuation of study treatment due to AEs. The overall summary tables will be repeated by age group as follows:

- ≥ 2 years to <12 years at randomisation (Visit 2)
- ≥ 12 years to <18 years at randomisation (Visit 2)

AEs/SAEs will be summarised by MedDRA SOC and MedDRA PT by actual study treatment received and by the same age group as previously defined. Events will be sorted by international order for system organ class (SOC) and alphabetically for PTs within each SOC. For each SOC/PT, the number (n) and percentage (%) of patients reporting at least one event at each level of summarisation (SOC/PT) will be presented ie, for a patient with multiple occurrences of the same AE, the event will only be counted once per PT/SOC. Patients with events in more than one SOC/PT are counted once per individual SOC/PT.

Most common AEs will be summarised separately by MedDRA PT, where most common is defined as a frequency $> 5\%$ in either of the two treatment groups and sorted by decreasing frequency based on the ticagrelor treatment group. Similarly, for presentation of non-serious AEs. In addition, AEs will be summarised by MedDRA PT and causality/relatedness. If a patient reports multiple occurrences of the same AE, the patient will be summarised only for the most related. Similarly, by MedDRA PT and maximum reported intensity. If a patient reports multiple occurrences of the same AE, the patient will be summarised only for the maximum reported intensity. In case of missing causality/relatedness and/or intensity, a missing category will be presented per relevant PT.

The event rate per 100 patient years will be presented by treatment group, where:

Event rate per 100 patient years = (number of patients with AEs/total exposure years) \times 100 (refer to Section 4.2.5).

Where:

Year = 360 days.

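### The overall AE and SAE tables count efficacy-endpoint crises as adverse events, with no version that leaves them out

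*SAP*

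**What the plan says.** Protocol 5.1.1.1 requires double recording: "A VOC occurring during the study should be recorded by the Investigator both as a primary endpoint event, and also as an AE". Protocol 6.3.9 fixes the AE term: "A VOC fulfilling the criteria should also be recorded as an adverse event with the diagnosis Sickle cell anaemia with crisis". SAP 3.2.1 repeats the double recording, on the VOC1 and AE eCRF pages. Under Protocol 6.2, in-patient hospitalisation makes an AE serious, so a hospitalised VOC is an SAE.

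On tabulation, SAP 4.2.9.1 states "Summary tables will include on-treatment/off-treatment AEs" and sets no exclusion for endpoint events. The overall tables, produced separately for on- and off-treatment AEs and repeated by age group, are described as "showing the number (n) and percentage (%) of patients with at least one AE in each of the following AE categories". The categories are "Any AE, any AE causally related to study treatment, maximum AE intensity, any AE with an outcome of death, any SAE", plus discontinuation of study treatment due to AEs. The same section defines a rate per 100 patient-years as the number of patients with AEs divided by total exposure years. It does not say whether this is one overall rate or a rate for each term. It also provides the breakdown: "AEs/SAEs will be summarised by MedDRA SOC and MedDRA PT by actual study treatment received".

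Protocol 8.5.4 likewise tabulates all AEs. The only special rule for SAEs that are also endpoints (Protocol 6.4.1) concerns reporting to health authorities, not tabulation.

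**The concern.** The safety objective (Protocol 2.3, SAP 1.1.3) is to assess the long-term safety and tolerability of ticagrelor against placebo. A patient enters the any-AE row by having a VOC, whatever else happens. If ticagrelor prevents VOCs, the row falls on ticagrelor with no difference in tolerability, and that fall can offset a real rise in other AEs. Even with no effect on VOCs, the row loses sensitivity, because most patients are already counted.

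The preferred-term tables do not restore the missing comparison. Patients overlap across terms, so the number with at least one non-VOC AE, or one non-VOC SAE, cannot be obtained by subtracting the VOC line.

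**Working it through.** **Inputs.** From Protocol 8.2 and SAP 1.3: negative binomial counts with shape k = 0.8; 2.0 VOCs per year on placebo; a 50% reduction, so 1.0 on ticagrelor; 1:1 allocation; 154 patients; two-sided 5% test; minimum follow-up 12 months, mean 18. Uniform enrolment over 12 months (Protocol 1.2.2) makes follow-up uniform on 12 to 24 months.

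**Does this reading of the shape parameter reproduce the stated 90% power?** Information per patient on the log rate is μ/(1 + μ/k). At a fixed 18 months:

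- placebo: 3.0/(1 + 3.0/0.8) = 0.632; ticagrelor: 1.5/(1 + 1.5/0.8) = 0.522
- variance with 77 per arm: 1/(77 × 0.632) + 1/(77 × 0.522) = 0.0455, so SE = 0.213
- ln 2/0.213 = 3.25, and 3.25 − 1.96 = 1.29, giving power 90.2%

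Averaging over 12 to 24 months gives 89.9%, and 5,000 simulated trials give 90.4%. Reading 0.8 as the dispersion gives 96.4% to 96.5%. So k = 0.8 is the negative binomial size.

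**Patients with at least one VOC.** P = 1 − (1 + rate × t/k)^(−k).

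| Follow-up | Placebo | Ticagrelor | Difference (points) |
|---|---|---|---|
| 12–24 months, averaged | 70.8% | 56.5% | −14.2 |
| 12 months | 63.3% | 47.7% | −15.6 |
| 6 months | 47.7% | 32.2% | −15.5 |

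The 6-month line is illustrative: SAP 3.1.4.1 records premature termination, so follow-up may be shorter than planned. The figures below use the first line and treat all follow-up as on-treatment.

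**Any-AE row.** The documents give no non-VOC AE rate. Assume a proportion q of patients has one, independent of VOCs. The row is then 1 − (1 − P)(1 − q), and with equal q the gap is 14.2 × (1 − q) points.

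| q, both arms | Placebo | Ticagrelor | Gap (points, before rounding) |
|---|---|---|---|
| 20% | 76.6% | 65.2% | −11.4 |
| 50% | 85.4% | 78.3% | −7.1 |
| 80% | 94.2% | 91.3% | −2.8 |
| 90% | 97.1% | 95.7% | −1.4 |

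**Masking.** Give ticagrelor a true 10-point excess of patients with a non-VOC AE:

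- 60% v 50%: 1 − 0.435 × 0.4 = 82.6% v 1 − 0.292 × 0.5 = 85.4%, shown as −2.8 points
- 80% v 70%: 91.3% v 91.2%, shown as +0.1
- 90% v 80%: 95.7% v 94.2%, shown as +1.5

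At q = 50% on placebo, the true excess must reach 16.4 points before the row is even level. If the drug had no effect on VOCs and both arms stood at 70.8%, a 10-point excess would shrink to 10 × (1 − 0.708) = 2.9 points.

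**Any-SAE row.** The documents do not give the share of VOCs that are serious (h) or of patients with another SAE (s). Assume h of 25% to 75%, applied as a thinning of the VOC rate, and s of 5% to 20%, equal in both arms.

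| h | s | Placebo | Ticagrelor | Gap (points) |
|---|---|---|---|---|
| 25% | 5% | 43.7% | 30.0% | −13.7 |
| 25% | 20% | 52.6% | 41.0% | −11.6 |
| 50% | 5% | 58.7% | 43.7% | −15.0 |
| 75% | 5% | 66.9% | 52.5% | −14.4 |
| 75% | 20% | 72.2% | 60.0% | −12.2 |

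Over the whole grid the row is 11.6 to 15.0 points lower on ticagrelor with no other difference.

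**The case against.** The best defence is that the plan already separates much of this. VOCs carry one mandated diagnosis and so should appear on an identifiable line. AEs are also shown by term with causality and with intensity, and those other lines do not depend on VOC counts. Bleeding, the main expected risk, has its own tables (SAP 4.2.9.3), as do transfusions, laboratory values and liver tests. SAEs and individual data are listed, so a determined reader could count non-VOC patients. Safety is descriptive (SAP 4.2.9), no decision rule rests on the overview, and showing all AEs is full disclosure. The SAP does not contradict the protocol.

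All of that stands, and it limits the importance of the point. It does not supply the patient-level summary that is missing: a reader of the tables alone cannot see how many patients had any AE or SAE other than the endpoint.

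Two stronger readings are tempting. A reader might take the 14-point difference in patients with a VOC as the apparent safety benefit in the any-AE row. It is only the upper bound, reached if no patient has any other AE. With open AE questioning at every contact (Protocol 6.3.5, Appendix E), q need not be low. A reader might also infer that the whole overview merely repeats the primary endpoint. The documents do not support that. Protocol Appendix A has deterioration from lack of effect rated as not related, which keeps most VOCs out of the causally-related row. Nothing shows that VOCs drive the death or discontinuation rows. The effect on maximum intensity is likely but cannot be sized, because no severity distribution is given and crises treated at home count as VOCs.

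**Conclusion.** The point holds in limited form. As written, SAP 4.2.9.1 mixes the efficacy endpoint into the any-AE and any-SAE rows, probably into maximum intensity, and into the rate per 100 patient-years if that is an overall rate. A per-term rate would leave the other terms untouched. The contamination is in counts of patients with an event, since that is what these tables report.

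The sizes depend on the planned 50% VOC reduction and on the assumed, independent background rates. For any AE the spurious gap runs from about 11 points down to about 1; for any SAE it stays at about 12 to 15 points across the assumed range. This is a gap in presentation that weakens the answer to the tolerability objective. It is not an error in the analysis, and the term-level and bleeding tables remain sound. It is worth correcting because the correction is cheap.

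**What to change.** Before unblinding, add to SAP 4.2.9.1 a repeat of the overall AE/SAE overview, including the age-group versions, and of the overall rate per 100 patient-years, placed beside the all-AE tables. State whether the planned rate is overall, per term or both. The repeat should:

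- exclude AEs linked to investigator-confirmed VOCs on the VOC1 eCRF;
- exclude AEs linked to acute SCD complications on the ASCD eCRF, which are also efficacy endpoints recorded as AEs (Protocol 6.3.9, SAP 3.3.4);
- keep potential VOCs that do not meet the definition, which Protocol 5.1.1.1 treats as ordinary AEs.

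No new data are needed. SAP 3.3.3 takes hospital dates for VOCs from the AE eCRF, so matching VOCs to their AE records is already required for hospitalised events. The cost is a few repeated tables with a filter. Nothing is removed, and specifying the filter before unblinding keeps it from being post hoc.

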3.1.7.1 On-treatment Period

The on-treatment period is defined as the period from first dose of study treatment up to and including last dose of study treatment + 7 days.

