3.4.1 Adverse Events

Serious adverse events will be collected from signing informed consent/assent, as relevant, throughout the treatment period and including the safety follow-up period. Adverse events will be collected from randomisation (Visit 2) throughout the treatment period and including the safety follow-up period. The Medical Dictionary for Regulatory Activities (MedDRA) (using the latest MedDRA version) will be used to code the AEs.

Adverse events will be categorised according to their onset date as follows:

- Pre-treatment: AEs occurring during screening ie, onset date < date of first dose of study treatment.
- On-treatment: AEs with onset date \geq the date of first dose of study treatment and \leq the date of last dose of study treatment + 7 days.
- Off-treatment: AEs occurring off-treatment ie, onset date > the date of last dose of study treatment + 7 days.

Although AE eCRF data collection mandates complete start/stop dates (or ongoing) for AEs collected following randomisation (Visit 2), in the exceptional case of missing/partial dates (and, as relevant, no indication of ongoing), no imputation will be done, and the event will be assumed to be "on-treatment" (worst-case approach). In case, for a specific event, severity or relationship is missing, no missing imputation will be performed, and a missing category will be presented in the relevant tables and listings.

Patients presenting clinical signs and symptoms consistent with COVID-19 infection will be managed as defined in Section 6.3.10 of the latest version of the CSP. Given the outcome of

the investigator's management of such patients AE/SAEs will potentially be identified as COVID-19 confirmed or suspected and will be presented as such in relevant safety analyses.

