4.2.2 Demographic and Baseline Characteristics

With reference to the general principles and definitions detailed in Sections 2.1, 3.1 and 4.1.1, demographic and baseline characteristics will be summarised using FAS, by treatment group and overall.

Demographic summary includes presentation of:

- Age (years)at randomisation (Visit 2)

- Age group at randomisation (Visit 2):
 - < 12 years
 - ≥ 12 years
- Sex
- Race
- Ethnicity
- Country

In addition, summary of patient characteristics includes presentation of:

- Baseline height (cm)
- Baseline weight (kg)
- Baseline body mass index (BMI):
 - Calculated as the ratio of patient's baseline weight (kg) to the square of the patient's baseline height (m): $BMI (kg/m^2) = (weight [kg]) / (height [m]^2)$

Where:

Height is collected in cm and will be converted to meters prior to calculating BMI by dividing by 100.

Similarly, summary of additional patient characteristics at baseline includes presentation of:

- ECG
- Seated pulse (beats/min)
- Malaria
- Eye examination
- Transcranial doppler

Patients' history of SCD will be characterised by summary of the following as collected on the SCDHIS eCRF:

- SCD genotype (HbSS/HbSB Thalassaemia)
- SCD history of complications
- Age (years) at diagnosis of SCD: Calculated as follows:
 - Age (years) at diagnosis = $(date\ of\ diagnosis - date\ of\ birth + 1) / 365.25$
- Number of years since SCD diagnosis: Calculated as follows:
 - Number of years since SCD diagnosis = $(date\ of\ randomisation\ [Visit\ 2] - date\ of\ diagnosis + 1) / 365.25$

Similarly, patients' history of VOC events will be characterised by summary of the following as collected on the VOC eCRF:

- Number of VOC events in past 12 months relative to screening (Visit 1) and categorised as:
 - ≤ 1 VOC event in the last 12 months relative to screening (Visit 1)
 - ≥ 2 to ≤ 4 events in the last 12 months relative to screening (Visit 1)
 - > 4 VOC events in the last 12 months relative to screening (Visit 1)
- Primary setting for VOC treatment
- Duration (days) from start of the last prior VOC event (prior to randomisation [Visit 2]) to randomisation (Visit 2): Calculated as:
 - Duration (days) = (date of randomisation [Visit 2] – start date of last prior VOC event) + 1

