4.2.5.1 Study Treatment Exposure

Total duration of study treatment exposure (days) by dose level and overall dose level (includes missed exposure days due to study treatment interruptions):

- Exposure (days) = (date of last dose of double-blind randomised study treatment – date of first dose of double-blind randomised study treatment) + 1

Where:

Date of first dose of double-blind randomised study treatment equals:

- Variable: *Start date of study drug administration*: Based on the EX eCRF, earliest administration date, at or after randomisation (Visit 2), at a given dose level and for each dose level received.
- By overall dose level: Overall earliest of the aforementioned first dose of study treatment administration dates, over all dose levels received.

Date of last dose of double-blind randomised study treatment equals:

- Variable: *End date of study drug administration*: As captured on the EX eCRF and is the latest administration date, on or after randomisation (Visit 2), at a given dose level and for each dose level received regardless of temporary study treatment administration discontinuation (study treatment interruptions).
- By overall dose level: Overall latest of the aforementioned last dose of study treatment administration dates, over all dose levels received. Patients may prematurely discontinue study treatment administration whilst continuing with scheduled assessments in the double-blind randomised treatment period. DOSDISC eCRF collects the variable, *date subject discontinued IP*. This date should equal the overall date of last dose of study treatment as captured on the EX eCRF but can be used in conjunction with EX data to accurately identify the overall date of last study treatment administration over all dose levels received in the double-blind randomised treatment period.

Total exposure years (across patients in a given treatment group) is defined as the sum of total double-blind randomised study treatment exposure (days) by overall dose level, including missed exposure days due to study treatment interruptions, for all patients in a given treatment group and is expressed in years as follows:

- Total exposure years (across patients) = Sum of (total study treatment exposure [days] by overall dose level)/360

Where:

Year = 360 days. .

Actual study treatment exposure (days) by dose level and overall dose level follows the same approach, however excludes all missed exposure days due to study treatment interruptions.

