4.2.6 Primary Efficacy Variable

4.2.6.1 Number of VOCs

The primary efficacy variable is the number of VOC events during the defined treatment period (refer to Section 3.1.4) and the primary analysis is to compare the VOC event rate of ticagrelor with placebo based on the intent to treat (ITT) principle. The primary efficacy analysis will be performed using FAS (refer to Section 2.1).

The null hypothesis is that the VOC event rate on ticagrelor is equal to the VOC event rate on placebo. The alternative hypothesis is that the VOC event rate on ticagrelor is not equal to the VOC event rate on the placebo, ie,

H_0 : Rate ratio (ticagrelor vs placebo) = 1

H_a : Rate ratio (ticagrelor vs placebo) \neq 1

The VOC event rate on ticagrelor will be compared to the VOC event rate on placebo using a negative binomial model for the primary analysis. The response variable in the model will be the number of VOC events experienced by a patient during the defined treatment period, regardless of premature discontinuation of study treatment. The model will include covariates of treatment group and baseline hydroxyurea use (Yes/No) as covariates.

The logarithm of the patient's observed follow-up time per defined treatment period expressed in years (where a year = 360 days) will be used as an offset term in the model to adjust for patients having different follow-up times.

The estimated treatment effect (ie, the rate ratio of ticagrelor versus placebo), the corresponding Wald 95% confidence interval (CI) and the p-value for the rate ratio will be presented. In addition, the VOC event rate and the corresponding 95% CI within each treatment group will be presented. The VOC event rate will be computed using the OM option in the LSMEANS statement of PROC GENMOD.

An estimated value of the rate ratio < 1 will favour ticagrelor. The estimated dispersion parameter will also be noted.

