4.2.6.2 Testing the Fit of Negative Binomial Distribution

The fit of the negative binomial distribution to the data will be tested by means of the Pearson goodness of fit test after estimating the parameters of the distribution and checking whether there are no convergence issues with the maximum likelihood estimation of the coefficients. The negative binomial model will be tested against the Poisson model in a likelihood ratio test to test the robustness of the model.

If the negative binomial distribution is not appropriate, a stratified Wilcoxon rank sum test will be used. As the stratified Wilcoxon rank sum test cannot be adjusted for the patient's follow-up time, the annualised number of VOC events will be used for the analysis rather than the number of VOCs as analysed for the primary efficacy. . By using annualised number of VOC events, it scales it allowing a comparison of VOC rates across patients with varying time in the study. Baseline hydroxyurea use (Yes/No) will be used as a stratification factor. Number of annualised VOC events is the count of VOC events experienced by a patient over the defined treatment period (refer to Section 3.1.5) as assessed by the investigator and collected on the VOC1 eCRF, multiplied by 360 days, and divided by the number of days in the defined treatment period.

$$\text{Num VOCs Annualised} = \frac{\text{Number of VOCs}}{(\text{defined treatment period end date} - \text{randomisation date}) + 1} * 360$$

A Wilcoxon rank sum test for each subgroup defined in Section 4.2.6.4 will also be presented. No stratification factor will be included in this analysis.

Median, median difference and 95% confidence interval for the median difference will be estimated using Hodges-Lehmann method. Summary statistics of the annualised VOC rate will also be presented.

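### The AE event rate per 100 patient-years divides patients counted once by person-time that does not stop at the first AE, so it is neither an event rate nor a first-event incidence rate

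*SAP*

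**What the plan says.** SAP 4.2.9.1 gives the formula "Event rate per 100 patient years = (number of patients with AEs/total exposure years", multiplied by 100, with a year of 360 days. The same section counts a patient once per term however often the AE recurs.

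The denominator comes from SAP 4.2.5 and 4.2.5.1. It starts from "Exposure (days) = (date of last dose of double-blind randomised study treatment" minus the date of first dose, plus 1. This is summed "including missed exposure days due to study treatment interruptions, for all patients in a given treatment group" and divided by 360. Nothing stops a patient's time at the first AE.

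The numerator window is longer. The on-treatment period in SAP 3.1.7.1 runs "up to and including last dose of study treatment + 7 days", and SAP 3.4.1 classifies AEs as on-treatment up to "the date of last dose of study treatment + 7 days". SAP 4.2.9.1 also tabulates off-treatment AEs, and the rate formula does not say which AEs it covers.

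The 360-day year appears in the VOC analyses too. In SAP 4.2.6.1 follow-up time "expressed in years (where a year = 360 days) will be used as an offset term in the model", and in SAP 4.2.6.2 the VOC count is "multiplied by 360 days, and divided by the number of days in the defined treatment period". The formula in SAP 4.2.2 headed "Number of years since SCD diagnosis: Calculated as follows" divides by 365.25, as does age at diagnosis.

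**The concern.** There are two standard rates per person-time. An event rate divides all events by all time at risk. A first-event incidence rate divides patients with an event by time up to the first event or the end of the window. The SAP pairs the numerator of the second with the denominator of the first. As an AE becomes common, the numerator approaches the number of patients while the denominator keeps growing, so the rate tends to a ceiling set by exposure rather than by the AE.

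This has two consequences. Ratios between arms are pulled towards 1 for common AEs. If exposure differs between arms, the formula can also show a difference when the hazards are equal, which an exposure-adjusted rate is meant to prevent.

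Common AEs are expected here. Protocol 5.1.1.1 and 6.3.9 require every VOC to be recorded as an AE as well, and Protocol 8.2 assumes 2.0 crises per year on placebo. Long-term safety and tolerability is a stated objective, and readers will take the table label literally.

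**Working it through.** **The SAP's own exposure figure.** The SAP prints no AE rate, but 4.2.5.1 has a worked example of exposure. From 18 April to 11 December 2019 inclusive is 238 days; less 9 missed days this is 229. Both figures reproduce. The AE rate uses the 238, with no stop at an AE and no added 7 days.

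**Inputs.** The planned follow-up is 12 to 24 months with mean 18 (Protocol 1.2.2), taken as exposure T uniform on 1 to 2 years. SAP 3.1.4.1 records early termination, so fixed exposures of 9 and 6 months are also shown. The documents give no AE hazards; a constant hazard λ per year is assumed over a range.

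**Formula as the SAP would compute it**, for on-treatment AEs:

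S(λ) = 100 × E[1 − exp(−λ(T + 7/365.25))] / (E[T] × 365.25/360)

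For 18 months' mean exposure the denominator is 1.5 × 365.25/360 = 1.522 years. With a constant hazard, both correct rates equal 100λ.

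| True rate per 100 PY | Patients with AE | SAP rate |
|---|---|---|
| 5 | 7.3% | 4.8 |
| 10 | 14.1% | 9.2 |
| 20 | 26.1% | 17.1 |
| 50 | 52.7% | 34.6 |
| 100 | 77.2% | 50.7 |
| 200 | 94.4% | 62.0 |

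At 20 per 100 PY, for example, 26.1/1.522 = 17.1. The ceiling is 100/1.522 = 65.7.

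**Displayed ratio when the true ratio is 2**, S(2λ)/S(λ), by true placebo rate per 100 PY:

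| Exposure | 1 | 5 | 10 | 20 | 50 | 100 |
|---|---|---|---|---|---|---|
| Uniform 12–24 months | 1.984 | 1.925 | 1.855 | 1.732 | 1.464 | 1.223 |
| 9 months | 1.992 | 1.962 | 1.926 | 1.857 | 1.681 | 1.463 |
| 6 months | 1.995 | 1.974 | 1.949 | 1.901 | 1.771 | 1.595 |

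For example, true rates of 20 against 40 print as 17.1 against 29.7.

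**Which feature does the damage.** Dropping the 7-day term and the 360-day conversion gives 1.735, 1.468 and 1.227 at 20, 50 and 100 (12–24 months). The lack of censoring accounts for essentially all of the compression.

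**Equal hazards, unequal exposure.** The assumption is every patient at 18 months in one arm and at 12 in the other:

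| True rate per 100 PY | 18 months | 12 months | Spurious ratio |
|---|---|---|---|
| 20 | 17.2 | 18.2 | 1.06 |
| 50 | 35.0 | 39.4 | 1.13 |
| 100 | 51.3 | 63.0 | 1.23 |

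With the same mean exposures but a one-year uniform spread in each arm, the ratios are 1.05, 1.12 and 1.21.

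**Window and year length for a rare AE.** The net effect on the absolute rate is (1 + 7/(365.25T)) × 360/365.25 − 1. This is +2.3% at 6 months, +1.1% at 9, +0.5% at 12, −0.2% at 18 and −0.5% at 24.

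**VOC rates.** 360/365.25 = 0.9856, so a true 2.00 per year prints as 2.00 × 0.9856 = 1.97. The factor is common to both arms and cancels in the rate ratio.

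**The case against.** The strongest reply is that the formula is fully disclosed. Patients with an AE over total exposure is a recognisable crude, exposure-adjusted patient incidence, so only the word event is certainly wrong. Counting patients once also matches Protocol 8.5.4. The rate is one descriptive figure beside counts and percentages, and SAP 4.2.9 rules out formal safety testing. Bleeding has its own event and patient counts (SAP 4.2.9.3), and VOCs have a count model with an offset. The compression figures rest on assumed hazards and, for the largest, on a follow-up plan that early termination has overtaken. Nothing suggests 18 against 12 months' exposure between arms randomised 1:1. The 360-day year is stated openly and used for every rate; 365.25 is used only for age and disease duration.

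Much of this stands, and it limits the severity: no test, stopping rule or sample size uses the rate; rare AEs are barely affected; the 7-day gap is immaterial for on-treatment AEs; and the unequal-exposure case is hypothetical. Two parts do not stand. The once-per-patient rule in Protocol 8.5.4 is for a proportion whose denominator is all patients in the safety set, so it does not justify a person-time denominator. And relabelling alone leaves the saturation for common AEs in place.

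**Conclusion.** The concern holds. Followed exactly, SAP 4.2.9.1 prints a mislabelled rate that understates common AEs and compresses their ratios. This is an error in the stated formula, and no other section corrects it.

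Its size depends on how common the AE is and how long exposure lasts. At placebo rates of 10 per 100 PY or less, a true ratio of 2 shows as 1.86 or more under all three exposure patterns. At 50 to 100 it shows as 1.46 to 1.22 with 12 to 24 months' exposure, and as 1.77 to 1.60 with 6 months. These figures assume constant hazards and the exposure patterns stated above.

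The window mismatch is minor for on-treatment AEs, but off-treatment AEs would have no person-time at all. The 360-day year makes absolute annual VOC rates and their confidence limits 1.4% too low and changes no ratio or p-value. Overall this is a minor to moderate reporting error that should be corrected; it does not threaten the primary conclusion.

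**What to change.** In SAP 4.2.9.1, replace the formula with one or both of the following, each labelled for what it is:

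- **Event rate:** on-treatment AEs divided by on-treatment person-time, from first dose to last dose + 7 days.
- **First-event incidence rate:** patients with the AE divided by person-time to the first such AE or the end of that window.

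Restrict the rate to on-treatment AEs, or give off-treatment AEs their own person-time. For clarity, also say whether the rate is given for any AE, by SOC or by PT.

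Use 365.25 days per year in SAP 4.2.5.1, 4.2.6.1, 4.2.6.2, 4.2.6.4 and 4.2.9.1.

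The cost is SAP wording and table programming before database lock. AE onset dates and dosing dates are already collected.
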